## **10.7 Pharmacokinetics Analyses**

To determine the PK profile of IVT injections at the different dose levels of QR-110, the following PK parameters will be calculated if sufficient data are available for each dose:

- $AUC_{0-\infty}$ : Area under the curve to infinity will be calculated based on the last observed concentration ( $C_{last}(obs)$ ) using formula:  $AUC_{0-\infty}=AUC_{last}+C_{last}(obs)/\lambda z$ , if feasible.
- $AUC_{0-t_{last}}$ : Area under the curve to the final sample with a concentration greater than lower limit of quantification (LLOQ) will be calculated based on the last observed concentration using the linear trapezoidal method.
- $C_{max}$ ,  $C_0$ : The maximum and minimum serum concentrations will be taken directly from the data.
- $T_{max}$ : Time to  $C_{max}$  will be taken directly from the data.

- $T_{1/2}$  (if measurable serum levels are obtained): The terminal elimination half-life will be estimated by non-linear regression analysis of the terminal elimination slope, if feasible.
- CL: Serum clearance will be estimated using the formula:  $CL = \text{Dose}/AUC_{0-\infty}$ .
- $V_d$  (if measurable serum levels are obtained and an elimination rate constant ( $\lambda_z$ ) is estimable): Apparent volume of distribution at steady state of the drug will be determined from trough levels.

Serum concentration below LLOQ prior to dose for the assay will be set to zero for the PK analysis. For other cases concentrations below LLOQ will be set for non-informative missing. Exact procedure for imputation of data will be described in the SAP.

All samples obtained from all cohorts will be analyzed to avoid bias in data presentation.

Sparse sampling analysis may be used to mitigate the risk of insufficient data to create individual profiles.

Drug concentrations will be summarized by nominal time point if 3 or more values are available. Descriptive statistics for PK parameters will be performed if  $\geq 50\%$  of subjects have evaluable data and number of values to summarize is  $\geq 3$ .

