PLR	Pupillary Light Reflex
PP	Per Protocol
PT	Preferred Term
RTF	Rich Text Format
SAE	Serious Adverse Event
SAP	Statistical Analysis Plan
SD	Standard Deviation
SDC	Statistics and Data Corporation, Incorporated
SOC	System Organ Class
$T_{1/2}$	Half-Life
TEAE	Treatment-Emergent Adverse Event
VA	Visual Acuity
V_d	Apparent Volume of Distribution
VEP	Visual Evoked Potential
VFQ-25	25-Item Visual Functioning Questionnaire
WHO DDE	World Health Organization Drug Dictionary Enhanced
WOCBP	Women of Childbearing Potential

1. Introduction

The purpose of this statistical analysis plan (SAP) is to describe the planned analyses and reporting in support of protocol PQ-110-001, version 6.0 dated 02-Aug-2018.

This SAP is being written with due consideration of the recommendations outlined in the most recent International Council for Harmonisation (ICH) E9 Guideline entitled Guidance for Industry: Statistical Principles for Clinical Trials and the most recent ICH E3 Guideline, entitled Guidance for Industry: Structure and Content of Clinical Study Reports.

This SAP describes the data that will be analyzed and the subject characteristics, efficacy, and safety assessments that will be evaluated. This SAP provides details of the specific descriptive statistical methods that will be used.

In addition to this SAP, inferential analyses will be generated by [REDACTED] which will also be used to support the CSR. The descriptions of methods and statistical analyses used for these inferential analyses are described separately within the scope of the Cytel SAP of which a copy has been included in whole in [REDACTED] and which should be read in conjunction with this SAP.

The statistical analysis methods presented in this document will supersede the statistical analysis methods described in the clinical protocol. If additional analyses are required to supplement the planned analyses described in this SAP they may be completed and will be identified in the Clinical Study Report (CSR). Study Objectives

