12.8 Clinical Laboratory Data

Clinical laboratory data including hematology, coagulation, serum chemistry and urinalysis are collected at specified visits. Other lab tests which are collected and will be summarized include Complement C4 NEPH, C-reactive protein (CRP), complement total, and erythrocyte sedimentation rate. The quantitative variables will be summarized by dose group and for all subjects with continuous descriptive statistics at each visit and time point where appropriate. The qualitative variables (counts and percentages) will be summarized by dose group and for all subjects at each visit and time point where appropriate. Change from baseline will also be summarized by dose group and for all subjects.

13. Pharmacokinetic Analyses

Pharmacokinetic (PK) analyses will be primarily performed on the PK population with observed data only. To determine the PK profile of IVT injections at the different dose levels of QR-110, the following PK parameters will be calculated if sufficient data are available for each dose:

- $AUC_{0-\infty}$: Area under the curve to infinity will be calculated based on the last observed concentration ($C_{last(obs)}$) using formula: $AUC_{0-\infty} = AUC_{last} + C_{last(obs)} / \lambda z$, if feasible.
- $AUC_{0-t_{last}}$: Area under the curve to the final sample with a concentration greater than lower limit of quantification (LLOQ) will be calculated based on the last observed concentration using the linear trapezoidal method.
- C_{max} , C_0 : The maximum and minimum serum concentrations will be taken directly from the data.
- T_{max} : Time to C_{max} will be taken directly from the data.
- $T_{1/2}$ (if measurable serum levels are obtained): The terminal elimination half-life will be estimated by non-linear regression analysis of the terminal elimination slope, if feasible.
- CL : Serum clearance level will be estimated using the formula: $CL = Dose / AUC_{0-\infty}$.
- V_d (if measurable serum levels are obtained and an elimination rate constant (λz) is estimable): Apparent volume of distribution at steady state of the drug will be determined from trough levels.

Serum concentration below LLOQ prior to dose for the assay will be set to zero for the PK analysis. For other cases concentrations below LLOQ will be set to one half of LLOQ.

All samples obtained from all cohorts will be analyzed to avoid bias in data presentation.

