Sparse sampling analysis may be used to mitigate the risk of insufficient data to create individual profiles.

Drug concentrations will be summarized by nominal time point if 3 or more values are available.

Descriptive statistics for PK parameters will be performed if $\geq 50\%$ of subjects have evaluable data and number of values to summarize is ≥ 3 .

Geometric means and coefficients of variation will be tabulated for C_{max} , C_0 , $AUC_{0-t_{last}}$, $AUC_{0-\infty}$, CL , and V_d for each dose group if possible. T_{max} will be summarized by median, minimum and maximum. Mean, standard deviation, minimum and maximum will be provided for $T_{1/2}$.

14. Efficacy Analyses

The Efficacy Evaluable population will be used for the efficacy analyses including mobility course, BCVA, FST, OCI, PLR and VFQ-25/CVAQC. Ocular imaging endpoints will also be summarized with the Efficacy population for all imaging endpoints including ERG imaging, SD-OCT (Photoreceptor Outer Segment Thickness, Full Retinal Thickness, ONL Thickness, Macular Edema), and NIRAF imaging. Selected efficacy endpoints which also constitute a safety outcome may be rerun using the Safety Population if the Efficacy Evaluable and Safety Populations differ. Tables will summarize endpoints using continuous or categorical descriptive statistics by visit and time point where appropriate. Change from baseline visit will be calculated as follow-up visit minus baseline visit. Tables will include sections for adults, pediatrics and combined cohorts according to dose groups.

Subject listings by visit, time point (when applicable) and eye will also be produced.

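### SAP Section 13 changes the rule for serum values below LLOQ from missing to LLOQ/2 without declaring it or keeping the substitutes out of the terminal-slope fit; separately, the zero rule for pre-dose values leaves the geometric mean of C0 without a fallback

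*SAP*

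**What the plan says.** SAP Section 13 has two rules for serum concentrations below LLOQ.

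- Pre-dose: "Serum concentration below LLOQ prior to dose for the assay will be set to zero for the PK analysis".
- All others: "For other cases concentrations below LLOQ will be set to one half of LLOQ".

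Protocol 10.7 has the same pre-dose rule, but for the remaining values it says: "For other cases concentrations below LLOQ will be set for non-informative missing". It also leaves the detail to the later document: "Exact procedure for imputation of data will be described in the SAP". SAP Section 1 states that its methods "will supersede the statistical analysis methods described in the clinical protocol".

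Section 13 opens with: "Pharmacokinetic (PK) analyses will be primarily performed on the PK population with observed data only". T1/2 is to be "estimated by non-linear regression analysis of the terminal elimination slope, if feasible". AUC0-inf adds the last observed concentration divided by lambda-z to the AUC up to the last quantifiable sample. CL is dose over AUC0-inf, and Vd needs an estimable lambda-z. AUC0-tlast ends at the final sample above LLOQ.

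For C0, which Section 13 describes as the minimum concentration and the protocol's abbreviation list as the trough: "Geometric means and coefficients of variation will be tabulated for" C0 among other parameters, for each dose group where possible. Protocol 10.7 has the same summary.

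SAP Section 15, which records departures from the protocol's analyses, covers the analysis populations and baseline only. The revision table in Section 17.1 does not mention LLOQ either.

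**The concern.** Under the protocol's rule a value below LLOQ cannot enter a regression. Under the SAP's rule it becomes a number, and every such value in a profile becomes the same number. A run of equal values at the end of a profile carries no information about elimination, only about the assay. If it is fitted as part of the terminal phase, lambda-z depends on where LLOQ lies, and T1/2, AUC0-inf, CL and Vd follow. Section 13 neither says that substituted values are left out of the fit nor sets a minimum number of quantifiable points.

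The C0 issue has a different source. A geometric mean is zero, or undefined on the log scale, as soon as one value is zero. Both documents assign zero to pre-dose values below LLOQ and then ask for that mean.

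Serum pharmacokinetics is a secondary objective and systemic exposure a secondary endpoint. Protocol 2.4 expects low systemic absorption, so values below LLOQ are likely. SAP 7.6 counts 11 subjects and Section 3 reports only two dose levels, so one distorted profile can move a group summary.

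**Working it through.** The plan states no figure to reproduce. The text available gives neither the LLOQ, the PK sampling times nor a half-life, so the following is an illustration on assumed inputs.

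**Half-life**

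Assumptions: samples at 2, 4, 8 and 24 h; mono-exponential decline without noise; 3 units at 2 h; true T1/2 of 4 h, with 12 h as a second case.

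Formula: C(t) = 3 × exp(−ln2 × (t − 2) / T1/2).

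- True T1/2 4 h: C = 3.000, 2.121, 1.061, 0.066.
- True T1/2 12 h: C = 3.000, 2.673, 2.121, 0.842.

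Each value below LLOQ is replaced by LLOQ/2, all four points are fitted, and T1/2 = ln2 / lambda-z. The SAP names non-linear regression, so the unweighted non-linear least-squares fit of A × exp(−kt) is the main result. The log-linear fit is shown because it is a common alternative.

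| LLOQ | Points ≥ LLOQ (true 4 h) | Non-linear, h | Log-linear, h | Points ≥ LLOQ (true 12 h) | Non-linear, h | Log-linear, h |
|---|---|---|---|---|---|---|
| 0.25 | 3 | 4.0 | 4.9 | 4 | 12.0 | 12.0 |
| 0.5 | 3 | 4.2 | 6.4 | 4 | 12.0 | 12.0 |
| 1 | 3 | 4.5 | 9.2 | 3 | 9.5 | 8.3 |
| 2 | 2 | 6.2 | 16.7 | 3 | 13.5 | 14.0 |
| 2.5 | 1 | 17.0 | 31.6 | 2 | 12.4 | 19.3 |

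The serum profile is the same down each half of the table; only the assay limit changes. With a true 4 h and three of four points quantifiable, the non-linear fit stays within 4.0 to 4.5 h. With two or one quantifiable it gives 6.2 and 17.0 h. With a true 12 h the error goes in both directions.

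Under the protocol's rule the fit returns the true 4.0 or 12.0 h wherever at least two points are quantifiable. With one point (LLOQ 2.5, true 4 h) no half-life can be estimated, whereas the LLOQ/2 rule reports 17.0 h there.

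**Parameters that follow from lambda-z**

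The extrapolated part of AUC0-inf is Clast / lambda-z = Clast × T1/2 / ln2, so it scales directly with the fitted T1/2. For a true 4 h it is inflated by 6.2 / 4 = 1.55 at LLOQ 2 and by 17.0 / 4 = 4.25 at LLOQ 2.5. CL falls as AUC0-inf rises. AUC0-tlast does not change, because trailing values lie beyond its end point.

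**Geometric mean of C0**

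Take five subjects with LLOQ = 1 and quantifiable values of 1.2.

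- One zero: (1.2⁴ × 0)^(1/5) = 0, whatever the other four are.
- One value at LLOQ/2 instead: (1.2⁴ × 0.5)^(1/5) = 1.01. If all five are below LLOQ the mean is 0.50, which is half the assay limit.

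The second case matters because the SAP does not say whether its pre-dose rule covers only the first dose or every dose. If only the first, later troughs below LLOQ take LLOQ/2 and the assay limit sets the mean. If every dose, a single such trough makes the mean unusable.

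**The case against.** Several stronger conclusions are tempting, and the documents do not support them.

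*The SAP was not free to change the rule.* It was. Protocol 10.7 hands imputation to the SAP and the SAP takes precedence. What stands is that the reversal is not declared where departures are listed.

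*Half-lives will be wrong by large multiples.* A reader could get such figures by adding samples below LLOQ at day 7 or month 1 and fitting log-linearly. But both documents name non-linear regression, and nothing visible places PK draws at those visits: the synopsis links serum sampling to the day after dosing. Under non-linear fitting the error is small when most of the profile is above LLOQ. The SAP also does not state that substituted values enter the fit; it only fails to exclude them. T1/2 and AUC0-inf are calculated only if feasible, and descriptive statistics need at least 3 values and at least 50% of subjects evaluable.

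*The missing rule exists nowhere.* Protocol 10.7 refers to a separate Pharmacokinetic Analysis Plan, which is not available here and may say how terminal points are chosen. That limits the claim to what the SAP says. A blanket LLOQ/2 rule in the SAP would still need to agree with that plan.

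*The SAP created the C0 problem.* It did not. The zero rule and the geometric mean are both in the protocol. The qualifier that means are tabulated where possible suggests that a set containing zeros would go unreported rather than be printed as 0, but it does not say what is reported instead.

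*LLOQ/2 plainly contradicts the observed-data statement.* That is one reading. The phrase, softened by its adverb, may only mean that missed samples are not filled in. The tension needs a clarifying sentence and is not evidence of error by itself.

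**Conclusion.** The concern holds in a conditional form. It is certain that the SAP replaces missing with LLOQ/2 for values that are not pre-dose, that Section 15 does not say so, and that Section 13 has no rule keeping substitutes out of the terminal fit. If they are fitted, the assay limit can drive T1/2, AUC0-inf, CL and Vd. In the assumed profile with a true T1/2 of 4 h, the result runs from 4.0 to 17.0 h by the SAP's named method and from 4.9 to 31.6 h log-linearly as LLOQ rises from 0.25 to 2.5. The non-linear error becomes material when only one or two points are quantifiable, which is plausible given the low exposure the protocol expects. These sizes rest on assumed sampling times, LLOQ, half-life and a noise-free mono-exponential profile.

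The C0 point is arithmetic and rests only on there being at least one trough set to zero. It belongs to both documents.

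PK is descriptive here and no decision rule depends on it, so this is a correction worth making before the PK tables are run and not a threat to the primary analysis.

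**What to change.** Amend SAP Section 13 as follows.

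- Exclude values below LLOQ after the last quantifiable sample from the lambda-z fit and from T1/2, AUC0-inf, CL and Vd, as protocol 10.7 implies, and check that the Pharmacokinetic Analysis Plan says the same. State a minimum number of quantifiable terminal points, for example 3.
- Use LLOQ/2 only in the concentration-by-time summaries.
- Say whether the pre-dose zero rule applies to the first dose only or to every dose, and what the observed-data statement covers.
- Summarise C0 by median, range and number below LLOQ in place of the geometric mean.
- List the change from the protocol's rule in Section 15 with a reason.

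The cost is a few sentences and a small change to the table shells. Fewer subjects will have an estimable half-life, and the PK tables should show how many were not estimable.

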14.1 Visual Acuity (BCVA) with ETDRS and BVRT

The logarithm of the minimum angle of resolution (logMAR) visual acuity is assessed using an EDTRS chart according to Section 3.5 of this SAP. Light perception (LP), detection of hand movement (HM) and ability to count fingers (CF) are also acceptable measures of visual acuity for this study. The Berkeley Rudimentary Vision Test (BVRT) will also be used to assess subjects' visual acuity. Since BCVA is an efficacy endpoint but also a safety output, this analysis will be produced primarily for the Efficacy Evaluable Population, and only repeated for the Safety Population if the Safety Population is different than the Efficacy Evaluable Population.

The observed value and change from baseline visual acuity will be summarized for each eye (treated eye and contralateral eye) for BCVA using continuous descriptive statistics on the logMAR scale by visit for each dose group and for all subjects. If there is no logMAR evaluation available from the EDTRS chart or BVRT assessment, visual acuity measures of LP, HM, and CF will be summarized using the following logMAR equivalents (refer to Section 21 Appendix 1 for full table):

- Light Perception = 4.0 logMAR
- Hand Movement = 3.0 logMAR
- Count Fingers = 2.0 logMAR

BVRT will be summarized in a similar manner as described for BCVA via ETDRS, with discrete summary statistics for frequency of Light Perception, Black White Discrimination, White Field Projection, and Cord Pair. The BVRT logMAR value will be summarized with continuous descriptive statistics. For BVRT, if the Light Perception question is not answered on the eCRF, then values will be imputed from the corresponding Best Corrected Visual Acuity (BCVA) Light Perception answer.

BCVA related AEs of special interest (AESI) will also be summarized with counts and percentages for each dose group and cohort with the definition of the BCVA related AESI according to Section 13.1.1 of the SAP. BCVA related AESI will include those TEAEs with MedDRA PTs of 'visual acuity reduced' or 'blindness'. In order to establish if results at individual visits resulted in an AESI report or not, the onset date of each reported AESI related to BCVA will be compared to dates of BCVA assessments, and assessments with dates between the onset date and resolution of the corresponding AESI will be flagged as having led to an AESI report.

A subject listing of visual acuity will also be produced. This BCVA listing will include a variable that indicates if a subject had a visual acuity change from baseline of ≥ 0.3 (15-letters or more) on the logMAR scale.

Shifts from baseline to post-BL in vision category will be summarized for BCVA using categories of LP, HM, CF and logMAR BCVA (i.e. visual acuity reported as better than CF), and for BRVT using categories of light perception, black white field discrimination, white field projection and logMAR BRVT (i.e. visual acuity better than light perception).

14.2 Red, Blue and White Full-Field Stimulus Testing (FST)

The Full-Field Stimulus Testing (FST) captures threshold measurements for each stimulus (red, blue and white light) that will be evaluated. Measurements with a Fail value of "0" are successful. A measurement with a Fail value of "1" is unsuccessful. If the threshold value fails, the next successful value will be captured. FST thresholds will be measured according to the imaging schedule of Section 3.5 of the SAP and Imaging Charter.

The FST values (ie, light sensitivity) and changes from baseline for each eye (treated eye and contralateral eye) will be summarized using continuous descriptive statistics and 95% CIs by visit and eye for each dose group and stimuli color for all subjects. Baseline FST is the average of all pre-dose FST assessments for that stimuli. Post-Baseline FST values are the average of all FST values for the given eye at a given time point and light color. An analysis of all failed and successful thresholds will be produced as well as an analysis of only successful thresholds. A subject listing of all failed and successful threshold FST will also be produced.

14.3 Pupillary Light Reflex (PLR)

Pupillary Light Reflex (PLR) imaging will measure the pupil size in various candela per square meter stimulus (ie, at 4, 40, 400 and 4000 cd/m^2). Maximum amplitude, delayed amplitude at 0.9 sec and overall latency (time to react) will be measured according to the imaging schedule of Section 3.5 of the SAP and Imaging Charter.

The PLR values and changes from baseline for each eye (treated eye and contralateral eye) will be summarized using continuous descriptive statistics and 95% CIs by visit and eye for each dose group and for all subjects. Baseline PLR is the average of all pre-dose PLR assessments. A subject listing of PLR will also be produced.

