### 2.1 Leber's Congenital Amaurosis

Leber's congenital amaurosis is a non-syndromic retinopathy that affects both cone and rod photoreceptor cells of the retina. It is a rare autosomal recessive disorder, reported to be the most severe and one of the earliest onset forms of vision loss in children, with detection of disease symptoms as early as the first year of life. The symptoms and signs include severe and early vision loss, sensory nystagmus (involuntary eye movements), abnormalities of pupil reactions, oculo-digital sign, and nondetectable photoreceptor electrical signals on electroretinogram (ERG). There are approximately 20 genes identified to date in which mutations are causative for LCA ([den Hollander 2008](#), [Estrada-Cuzcano 2011](#), [Kmoch 2015](#)), and the LCA classification is based on the disease causing gene. The most frequently mutated LCA gene is *CEP290*, with mutations accounting for about 15% to 30% of LCA cases ([Coppieters 2010](#), [den Hollander 2008](#), [den Hollander 2006](#), [Perrault 2007](#), [Stone 2007](#)).

The *CEP290* gene is located on the long (Q) arm of chromosome 12 and codes for CEP290 protein, which has an important role in centrosome and cilia development. The most frequently occurring *CEP290* mutation associated with retinal dystrophy in Caucasians, especially in European countries and the United States (US), is a change in intron 26 of the *CEP290* gene (p.Cys998X) ([Stone 2007](#), [den Hollander 2006](#), [Perrault 2007](#), [Littink 2010](#)). This mutation creates a cryptic splice donor site in intron 26 which results in the inclusion of an aberrant exon (exon-X) of 128 bases in the mutant *CEP290* messenger ribonucleic acid (mRNA). This cryptic exon introduces a premature stop codon, predicted to render CEP290 a truncated protein. The mutation has been found in homozygosity or compound heterozygosity in patients with *CEP290* LCA ([Cideciyan 2007](#), [den Hollander 2006](#), [Perrault 2007](#)). Both the homozygous and heterozygous genotypes result in a similar clinical presentation. The *CEP290* p.Cys998X

mutation appears to be hypomorphic in nature, with wild-type transcripts present in peripheral tissues, explaining the non-syndromic nature of the *CEP290* p.Cys998X mutation ([Parfitt 2016](#)).

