##### **4.1.2 Secondary Endpoints**

- Frequency and severity of non-ocular AEs
- Changes in ophthalmic examination findings
- Change in BCVA
- Changes in infrared imaging
- Changes in OCT findings
- Changes in safety parameters, including vital sign measurements, physical examination findings, electrocardiogram (ECG) and laboratory parameters

- Characterize the PK profile of QR-110 in serum
- Change in light sensitivity to red FST
- Change in light sensitivity to blue FST
- Change in amplitude to white PLR
- Change in latency to white PLR

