1.5 Secondary Endpoints

- Frequency and severity of non-ocular Adverse Events (AEs)
- Changes in ophthalmic examination findings
- Change from baseline in Best-Corrected Visual Acuity (BCVA) in treated eye and contralateral eye
- Change from baseline in near-infrared autofluorescence (NIRAF) data in treated eye and contralateral eye:
 - Horizontal diameter
 - Vertical diameter
 - Area
- Changes in SD-OCT findings in treated eye and contralateral eye with horizontal and vertical scan for:
 - Change from baseline in full retinal thickness (FRT) at foveal pit
 - Change from baseline in mean FRT (line scan)
 - Change from baseline in outer nuclear layer (ONL) thickness at foveal pit
 - Change from baseline in extent of ONL region
 - Change from baseline in photoreceptor outer segment thickness (OST) at foveal pit
 - Change from baseline in mean photoreceptor OST (line scan)
- Changes in safety parameters, including vital sign measurements, physical examination findings, electrocardiogram (ECG) and laboratory parameters
- Systemic exposure of QR-110 in serum
- Change from baseline in light sensitivity to red Full-field Stimulus Testing (FST) in treated eye and contralateral eye
- Change from baseline in light sensitivity to blue FST in treated and contralateral eye
- Change from baseline in white Pupillary Light Reflex (PLR) at 4 levels of illumination (ie, 4, 40, 400, and 4000 cd/m²) in treated eye and contralateral eye:
 - Pre-stimulus
 - Maximum amplitude
 - 0.9 seconds amplitude
- Overall latency (time to react)

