7.2 Missing or Inconclusive Data Handling

Other than the imputations described within Section 7.2.1, no special handling of missing data will be made and analyses will be conducted using observed values only.

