7.2.1 MISSING MOBILITY COURSE COMPOSITE SCORE IMPUTATIONS FOR CENTRAL READING CENTER GRADING

7.3 Definition of Baseline

Baseline is defined as the last measurement prior to the first dose of study drug in the treated eye for IOP, laboratory parameters, and the safety endpoints slit lamp biomicroscopy, posterior segment/fundus exam, vital signs, and ECG . For ophthalmic parameters BCVA, FST, mobility course, OCI and PLR measured at Screening and Visit 2 (Day 1) the average will be defined as baseline. For other ophthalmic parameters, NIRAF, SD-OCT, and ERG, planned to be done once at baseline, the average will be defined as baseline if the exam is repeated. Change from baseline will be calculated as follow-up visit/time point minus baseline visit/time point.

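### An eye that gains or loses its pupil reaction drops out of the PLR latency change, and the visible SAP has no rule that would show it

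*SAP*

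**What the plan says.** Protocol 4.1.2 lists "Change in latency to white PLR" among the secondary endpoints, and SAP 1.5 repeats it as a change from baseline. SAP 14.3 describes the measures as follows: "Maximum amplitude, delayed amplitude at 0.9 sec and overall latency (time to react) will be measured according to the imaging schedule". On analysis it says: "The PLR values and changes from baseline for each eye (treated eye and contralateral eye) will be summarized using continuous descriptive statistics", with 95% confidence intervals, by visit and dose group. SAP 7.3 and 14.3 make the PLR baseline the average of the pre-dose assessments.

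For missing data, SAP 7.2 says "no special handling of missing data will be made and analyses will be conducted using observed values only". Its one exception, 7.2.1, is headed "MISSING MOBILITY COURSE COMPOSITE SCORE IMPUTATIONS FOR CENTRAL READING CENTER GRADING" and does not concern PLR.

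The visible text of 14.3 gives no code, category, count or rank for an eye that does not react. It also gives no rule for the baseline average when one pre-dose test shows a reaction and the other does not. Elsewhere the SAP does deal with results that fall off the scale. SAP 14.2 analyses FST thresholds with and without failed measurements. SAP 14.1 gives logMAR values to light perception, hand movement and counting fingers, and adds a shift table by vision category.

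**The concern.** Latency exists only if there is a reaction to time, so whether the value is missing depends on the outcome itself. An eye silent at baseline that reacts after dosing has made perhaps the largest gain possible on this test, yet it has no baseline to subtract. An eye that stops reacting has perhaps the largest loss, yet it has no follow-up value. Both are left out of the change summary. The gained eye does enter the later visit mean, where a slow new latency pulls that mean up. The lost eye leaves it.

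Non-reaction is foreseeable: Protocol 2.1 names "abnormalities of pupil reactions" among the signs of the disease. Protocol 2.3.1 also counts PLR among the objective tests when it justifies an open-label design without sham injections, so a reader will give weight to the PLR tables.

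**Working it through.** The plan gives no figure on this point and its sample size is not power-based, so there is nothing to reproduce. The check applies the SAP's own rules to a small example.

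**Inputs from the documents.** Latency is a time to react (SAP 14.3). Only observed values are used (SAP 7.2). Change is follow-up minus baseline (SAP 7.3). There were 11 subjects at the second interim analysis (SAP 7.6). Summaries are by dose level, for adults, children and both combined (SAP 7.4), and two dose levels were used (SAP 3). That gives four cohorts, or 11/4 = 2.75 subjects per cohort on average.

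**Assumed inputs (not in the documents).** Six treated eyes. Five react at 400 ms throughout; the sixth has a latency of 600 ms whenever it reacts.

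**Step 1: the planned summaries.**

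- The mean over six reacting eyes is (5 x 400 + 600)/6 = 433.3 ms; over the five steady eyes it is 400.0 ms.
- The paired change uses only eyes with both values. In the first two rows below these are the five steady eyes, so it is 0.0 ms.
- In the third row those five eyes also speed up by 10 ms.

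| Sixth eye | Baseline mean (n) | Follow-up mean (n) | Difference of visit means | Paired change (n) |
|---|---|---|---|---|
| Gains a reaction | 400.0 (5) | 433.3 (6) | +33.3 ms | 0.0 ms (5) |
| Loses its reaction | 433.3 (6) | 400.0 (5) | -33.3 ms | 0.0 ms (5) |
| Loses it; other five 10 ms faster | 433.3 (6) | 390.0 (5) | -43.3 ms | -10.0 ms (5) |

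In the first two rows the difference of visit means points the wrong way, while the paired change shows nothing.

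**Step 2: the same eyes with non-reaction set to a ceiling C** (assumed 900, 1500 or 3000 ms).

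- Gain: mean change (600 - C)/6 = -50, -150 or -400 ms.
- Loss: (C - 600)/6 = +50, +150 or +400 ms.
- Loss with the other five 10 ms faster: (-50 + C - 600)/6 = +41.7, +141.7 or +391.7 ms, against a paired change of -10.0 ms. Here the sign does reverse.

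The size depends wholly on C, so a single imputed number is no sound repair. A median is not enough either: in the last case the median change is -10.0 ms at every C, and the lost eye stays invisible.

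**Step 3: range for the visit mean.** If one of n eyes newly reacts at L ms and the others stay at 400 ms, the mean shifts by (L - 400)/n. For L from 450 to 800 ms:

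- n = 4: +12.5 to +100.0 ms
- n = 6: +8.3 to +66.7 ms
- n = 11: +4.5 to +36.4 ms

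**Step 4: chance that it happens at all.** If each of 11 eyes switches independently with probability p, the chance of at least one switch is 1 - (1 - p)^11. For p = 5%, 10% and 20% (assumed) this is 43%, 69% and 91%.

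**The case against.** The strongest answer is that the endpoint is a change from baseline, not a difference of visit means. A reader might infer that the planned endpoint shows worsening when eyes improve. The documents do not support that in general: the paired change omits the switching eye, and reads 0.0 ms in the first two rows of the table. It reverses only if the remaining eyes move against the eye that switched. This objection stands and limits the claim.

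Much of the rest also stands.

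- **Frequency.** Abnormal pupil reactions are not absent ones, and no frequency is given.
- **Definition.** SAP 1.5 sets latency apart from the measures listed under the four illumination levels, and 14.3 calls it overall. If it is derived across levels, silence at a dim level need not make it missing.
- **Other outputs.** Amplitude is a companion secondary endpoint, and no constriction may be recorded there as about zero. SAP 7.4 reports n and the median, and 14.3 promises a subject listing. With 11 subjects a switch could be traced.
- **Unseen text.** The Imaging Charter, the separate inferential SAP and the responder analysis noted in the SAP's revision history cannot be read here. Any of them may code non-reaction.
- **Weight.** The analyses are exploratory, with no multiplicity control and no inferential testing under this SAP.

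These points soften the harm but do not repair the latency table. A smaller n does not tell a lost reaction from a missed or unusable test, and a listing is not a summary.

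**Conclusion.** The concern holds in a limited form. Read as written, SAP 7.2 and 14.3 exclude from the latency change exactly those eyes whose reaction appears or disappears, and average each visit over whichever eyes happened to react. Large gains and losses are hidden. Visit means can mislead in direction; the paired change does so only when the remaining eyes move the opposite way.

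In the assumed example one switching eye moves the visit mean of six eyes by 33.3 ms either way. The true size cannot be given, because latencies and the frequency of non-reaction are not in the documents. The conclusion rests on reading a time to react as undefined without a reaction, which follows from the term but is not stated outright. It is a finding about the visible SAP, not proof that no rule exists elsewhere.

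The harm is to the interpretation of a secondary endpoint, not to error control. It should be corrected, but it does not threaten the trial.

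**What to change.** In SAP 14.3:

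1. Define non-reaction, and keep it separate from a failed or unusable recording. Protocol 2.5 expects severe nystagmus in many subjects to hamper OCT measurement; if PLR recordings also fail, counting them as non-reaction would add a bias of its own. State how the baseline average is formed when pre-dose tests disagree, and whether overall latency is per illumination level.
2. Tabulate the number of eyes with a reaction, and the gained and lost shifts from baseline, by eye, visit and dose group, and by illumination level if latency is per level.
3. Label the mean latency change as conditional on reacting at both times, with its n.
4. Add a sensitivity summary that gives true non-reaction the worst rank and shows each eye as improved, unchanged or worsened. Give a median only where it is defined: with three of six eyes silent it falls between a number and no response.

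If the Imaging Charter or the inferential SAP already codes non-reaction, cite that rule in 14.3.

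The cost is SAP wording and small tables, with no change to trial conduct. This assumes that presence or absence of a reaction can be taken from the existing recordings, which the documents do not state.
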